## **Protocol Version History**

Protocol Version	Version Date	Summary of Revisions Made	Rationale
1.0	12/13/2019	Initial version	
2.0	10/30/2020	Revised Cognitive Battery, UW ADRC Recruitment letter added, Study Partner Questionnaires added to study visits, Study Partner Questionnaires description added, Study Partner compensation added, Quality of Life Questionnaires removed from study visits and secondary endpoints, exclusion criteria updated to reflect need for study partner, Study Visit Calendar updated to reflect changes	
3.0	01/13/2021	Moved follow-up MRI to Month 3, expanded visit windows, 3.1 Objectives changed, Table 3.2 updated, 6.0 and 12.1 secondary endpoints updated	Follow-up MRI moved to Month 3 as we expect long-term effects of this multifield extended approach to tDCS, expanded visit windows to account for potential COVID-19 disruptions and increased subject retention

4.0	04/15/2021	
 
1. Increased subject recruitment to 20 subjects and study partners,
 
2. removed handedness from inclusion/exclusion criteria,
 
3. increased Day 1 visit window to 6 months,
 
4. removed Day 1 AE evaluation,
 
5. added potential for subject interchangeability between sites
 
6. formatting modifications
 
	
 
1. Increased recruitment number to account for screen fails and withdrawals
 
2. Revised inclusion/exclusion criteria to improve recruitment
 
3. Day 1 visit window extended to improve subject retention
 
4. Day 1 AE evaluation removed as visit occurs prior to tDCS/sham administration
 
5. Interchangeability between sites added to improve subject retention and dataset completion
 
6. Formatting modifications to improve readability
 

5.0	10/15/2021	
 
1. Section 8.5 – modified to include reimbursement for hotel or other form of lodging. MCW subjects may be eligible to stay at Kathy's House
 
	
 
1. We are offering lodging assistance to improve enrollment and retention
 

## 2.0 LIST OF ABBREVIATIONS

ADCS-PACC	Alzheimer's disease cooperative study Preclinical Alzheimer Cognitive Composite
AE	Adverse Event
CCC	Clinical Coordinating Center
CFR	Code of Federal Regulations
CRF	Case Report Form
CRO	Contract Research Organization
CT	Cognitive Training
CTCAE	Common Terminology Criteria for Adverse Events
CTMS	Clinical Trial Management Software
DCC	Data Coordinating Center
eCRF	Electronic Case Report Forms
EDC	Electronic Data Capture
FDA	Food and Drug Administration
GCP	Good Clinical Practice
HD-tDCS	High Definition Transcranial Direct Current Stimulation
HIPAA	Health Insurance Portability and Accountability Act
IDE	Investigational Device Exemption
ICTR	Institute for Clinical and Translational Research
IRB	Institutional Review Board
MCI	Mild cognitive impairment
MOP	Manual of Procedures
NIH	National Institutes of Health
MRI	Magnetic resonance imaging
OHRP	Office for Human Research Protections
OnCore	Online Collaborative Research Environment
PHI	Protected Health Information
PI	Principal Investigator
POC	Point of Contact
SAE	Serious Adverse Event
SAP	Statistical Analysis Plan
sIRB	single IRB
SMART IRB	Streamlined, Multisite, Accelerated Resources for Trials IRB
SMP	Study Monitoring Plan
SMS	Study Monitoring Service
UP	Unanticipated Problem

### 3.0 STUDY SUMMARY

#### 3.1 Synopsis

Full Title	A Randomized, Double-Blinded, Placebo Controlled Pilot Trial of the Feasibility of High Definition Transcranial Direct Current Stimulation and Cognitive Training in Patients with Mild Cognitive Impairment.
Short Title	A pilot study of HD-tDCS and cognitive training to improve cognitive function in MCI
Protocol Number	00035757
Number of Site(s)	Two clinical sites in the United States
Phase	Pilot trial
Main Inclusion Criteria	
 
1. Age <math>\geq</math>50-90 years
 
2. Willing and able to undergo all procedures
 
3. Retains decisional capacity at initial visit
 
4. Meets criteria for MCI, amnestic type (Petersen, 2004).
 

Main Exclusion Criteria	
 
1. Significant kidney injury requiring hemodialysis
 
2. Automatic Internal Cardiac Defibrillator (AICD) or Pacemaker
 
3. Significant congestive heart failure
 
4. History of clinically significant ischemic or hemorrhagic stroke, or lacune or infarct considered by radiologist likely to cause or contribute significantly to cognitive symptoms
 
5. History of thalamic lacunar stroke
 
6. Modified Hachinski Ischemia Score <math>></math>4 points
 
7. History of seizure disorder requiring medication
 
8. History of brain surgery (for seizure disorder, aneurysms, or benign/malignant tumor)
 
9. History of HIV/AIDS
 
10. Severe untreated obstructive sleep apnea
 
11. Greater than three servings alcohol daily or illicit drug use
 
12. Major neurologic disorders other than dementia (e.g., MS, ALS)
 
13. Schizophrenia, bipolar disorder, other serious mental illnesses
 
14. Other significant medical conditions at investigators' discretion
 
15. Pregnancy
 
16. Lack of study partner (Participants are allowed to find a new study partner if the original study partner withdraws)
 

Endpoints	
Primary Endpoint
 
 
• Treatment completion rate.
 
 
Secondary Endpoints

[figure not shown]
	
 
• Consent rate
 
• ADCS PACC score at 3 and 6 months
 
• Neurite density (intracellular volume fraction) at 3 months
 
• Diffusivity indices: Fractional anisotropy (FA), Mean (MD), Axial (AD), Radial (RD)
 
• Diffusivity at 3 months
 
• Morphometric indices: Cortical thickness, Surface Area, Volume, gyration index at 3 months.
 
• ASL perfusion indices: blood flow, blood volume, mean transit time, time to peak, at 3 months
 

Study Design	The study design is a double-blinded, randomized pilot clinical trial of HD-tDCS/sham HD-tDCS combined with CT, administered to subjects with amnestic MCI (aMCI) in blocks of 5 daily treatments for a total of 15 sessions. There will be one treatment block/month for a total of 3 months. 20 participants with aMCI will be enrolled. There will be 2 treatment groups/arms with 10 subjects per group/arm. We anticipate a dropout rate of appr. 10% and aim to complete procedures in 20 subjects.
Study Intervention	High definition transcranial direct current stimulation (HD-tDCS) Sham HD-tDCS Computerized Cognitive training (CCT) Sham CT
Total Number of Subjects	20
Study Population	Male and females aged 50 to 90 years with established diagnosis of MCI amnestic type. Total of 20 subjects
Statistical Methodology	Given the pilot nature of this study, two feasibility outcomes will be included: Consent rate and treatment completion rate. 20 patients are enough to calculate a 90% exact binomial confidence interval of (.75, 1) if all 20 are observed to complete treatment. Thus, this sample size is large enough to potentially exclude completion rates of 3/4 or lower. The pilot data from this study will provide initial estimates of the variability and the effect sizes. This information will then be used for the formal calculations of power and sample size necessary to conduct a future phase II trial.
Estimated Subject Duration	The duration of the study for each subject is approximately 6 months.
Estimated Enrollment Period & Study Duration	Study enrollment and follow-up will occur over 9 months with the total expected duration of the trial to be 12 months.

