## Recruitment outline

This is a multisite trial. Participating sites are the Medical College of Wisconsin, Milwaukee, and the University of Wisconsin, Madison.

	UW-Madison Site (n=10)		MCW Site (n=10)	
	Baseline	Treatment and Follow-Up	Baseline	Treatment and Follow-Up
aMCI	10	10	10	10
Total	10	10	10	10

**Table 2:** Recruitment outline

**Information about subjects** will be obtained from medical records, surveys, interview questions, data collection forms, and imaging studies.

**Expected duration of intervention** is 3 months for each subject and **expected duration of participation** in the trial is 6 months.

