## 7.2 End of Study Definition

End of study will occur when 20 subjects have completed this pilot project.

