### **8.4 Subject Recruitment**

A total of 20 subjects will be recruited from two sites in the United States. Several recruitment strategies may be employed, and sites may use a combination of methods depending on their capabilities. Possible recruitment strategies are as follows (non-comprehensive list):

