## **8.6 Early Termination and Withdrawal**

Subjects are free to withdraw from participation in the study at any time upon request.

The Principal Investigator (PI) may discontinue or withdraw a subject from the study for the following reasons at his/her discretion:

- Pregnancy
- Subject non-compliance with study requirements (e.g., study intervention non-compliance)
- If any clinical adverse event (AE) or other medical condition or situation occurs such that continued participation in the study would not be in the best interest of the subject
- If the subject is no longer an appropriate candidate for participation
- There is evidence of progressive disease or unacceptable toxicity
- Subject unable to receive scheduled intervention for 3 weeks

Subjects who sign the informed consent form and are randomized but do not receive the study intervention will be replaced. Subjects who sign the informed consent form, are randomized and receive the study intervention, then subsequently withdraw, or are withdrawn or discontinued from the study, will not be replaced.

The following actions should be taken if a subject withdraws, or fails to return for a required study visit:

- The site will attempt to contact the subject and reschedule the missed visit within 6 weeks and counsel the subject on the importance of maintaining the assigned visit schedule and ascertain if the subject wishes to and/or should continue in the study.
- Before a subject is deemed lost to follow-up, the investigator or designee will make every effort to regain contact with the subject where possible, 3 telephone calls and, if necessary, a certified

letter to the subject's last known mailing address or local equivalent methods. These contact attempts shall be documented in the subject's medical record or study file.

- If the subject continues to be unreachable, they will be considered to have withdrawn from the study with a primary reason of lost to follow-up. The withdrawn date is the last day of attempted contact.

The study team will attempt to obtain the following information from subjects following early termination or withdrawal: Adverse events and reason for withdrawal.

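### With 20 enrolled, about 10% dropout and no replacement after treatment, one treated withdrawal makes the 20-completer aim and the end-of-study condition unreachable; whether replaced subjects count in the completion rate is unstated

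*Combined protocol and SAP*

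**What the plan says.** - **Numbers in.** Section 3.1: "20 participants with aMCI will be enrolled", with 10 per arm and a total of 20. Section 8.4: "A total of 20 subjects will be recruited from two sites in the United States".
- **Numbers out.** Section 3.1, in one sentence: "We anticipate a dropout rate of appr. 10% and aim to complete procedures in 20 subjects".
- **End of study.** Section 7.2: "End of study will occur when 20 subjects have completed this pilot project".
- **Replacement.** Section 8.6: "Subjects who sign the informed consent form and are randomized but do not receive the study intervention will be replaced". Those who have received the intervention and "then subsequently withdraw, or are withdrawn or discontinued from the study, will not be replaced".
- **Precision.** Section 3.1, repeated in 12.2: "20 patients are enough to calculate a 90% exact binomial confidence interval of (.75, 1) if all 20 are observed to complete treatment". No other result is given an interval.
- **Completer.** Section 9.4 requires all stimulation-plus-training sessions and cognitive testing at 0, 3 and 6 months, and links this to the primary outcome, the treatment completion rate. It does not say which subjects form the denominator.
- **Timing.** The study calendar (10.1) places randomisation at the baseline visit, whose window is -6 months, so loss between randomisation and first treatment is possible. No section says when the 10% dropout is expected.

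**The concern.** The same figure, 20, is the number enrolled and the number meant to finish, although the plan expects to lose about one subject in ten. The replacement rule closes the gap only for losses before treatment. For losses after treatment nothing brings the count back to 20, so the end-of-study condition could never be met as written.

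The primary endpoint is also affected. Section 12.2 rests its feasibility argument on excluding completion rates below 75%, and shows this only for a result without any loss. A reader cannot see what 20 subjects would show at the result the plan itself expects.

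Replacement raises a further question. A subject who is randomised, never treated and then replaced is a feasibility loss. If such subjects are left out of the completion rate, that loss disappears from the primary result. The plan does not say which way they are counted.

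**Working it through.** **Inputs.** 20 subjects and about 10% dropout (3.1); the replacement rule (8.6); the 90% exact interval (3.1, 12.2). Assumed, because the plan is silent: the share *s* of dropout that occurs before first treatment; independent subjects; replacement continues until 20 are treated; every retained subject completes.

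**1. The plan's own interval.** For *n* completers out of *n*, the exact (Clopper-Pearson) lower limit is (α/2)^(1/n) two-sided and α^(1/n) one-sided. With n = 20 and α = 0.10:
- two-sided: 0.05^(1/20) = .861
- one-sided: 0.10^(1/20) = .891

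The printed .75 is reproduced by neither. The true interval is narrower, so the statement that 20/20 excludes 75% still holds. Recomputed limits are used below.

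**2. Expected completers.** With total dropout *d*:
- probability of completing once treated = (1 − d)/(1 − ds)
- expected number randomised to obtain 20 treated = 20/(1 − ds)

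At d = 0.10:

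| Share before treatment | Randomised | P(complete, if treated) | Expected completers | P(20/20) | P(19 or more) |
|---|---|---|---|---|---|
| none | 20 | .900 | 18.0 | .900^20 = 12% | 39% |
| half | 20/.95 = 21.1 | .90/.95 = .947 | 18.9 | .947^20 = 34% | 72% |
| all | 20/.90 = 22.2 | 1 | 20 | 100% | 100% |

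Twenty completers are expected only in the last row, and there about 22 are randomised, not 20.

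Sensitivity to the dropout rate, 5% to 15%: with all loss after treatment, 19 to 17 completers and P(20/20) from 36% to 4%; with half before, 19.5 to 18.4 completers and P(20/20) from 59% to 18%.

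**3. Precision at the results the plan expects.** Exact two-sided 90% intervals:

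| Result | Interval | Excludes 75%? |
|---|---|---|
| 18/20 | .717 to .982 | no |
| 19/20 | .784 to .997 | yes |
| 20/20 | .861 to 1 | yes |

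With all loss after treatment, the chance of a result that excludes 75% is therefore the 39% in step 2.

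**4. Effect of the denominator.** The number replaced is assumed to be one or two. Two-sided lower limits:
- 20 completers: .861 for 20/20, .793 for 20/21, .741 for 20/22
- 19 completers: .784 for 19/20, .729 for 19/21

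One replaced subject leaves the conclusion about 75% unchanged with 20 completers but reverses it with 19. Two reverse it with 20. In expectation, the rate among treated subjects is 90%, 95% or 100% in the three rows of step 2. Among all randomised it is 90% in each (18/20, 18.95/21.05, 20/22.2).

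**The case against.** **The completer figure is only an aim.** That is fair for the synopsis sentence. Section 7.2, however, is the definition of when the study ends. Reading completion there as merely having ended participation would remove the conflict, but the text does not say so, and 3.1 speaks of completing procedures.

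**Dropout is not the same as non-completion.** This stands, and it limits the figures. Under 9.4 a retained subject with a missed session is not a completer; 10.2 allows missed sessions to be made up before the Month 3 procedures. Sessions missed and not made up would lower the probabilities above. Conversely, 12.2 speaks of completing treatment, which a subject lost after the last session has done. The percentages are dropout-based.

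**The precision statement is openly conditional on 20/20.** True, and an interval given with two limits is ordinarily two-sided. On a one-sided reading the lower limit at 18/20 is .755, which does exclude 75%. The gap is that the only result shown is an unlikely one unless most loss precedes treatment.

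**Intent-to-treat settles the denominator.** Section 12.3 concerns a future phase II trial, and 12.4 reaches this trial only as appropriate. Counting all randomised subjects is a sound choice, but the documents do not make it.

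Two stronger readings should be resisted. Table 2 shows 10 at baseline and 10 at treatment and follow-up per site, and a reader might infer a forecast of no loss; it is a recruitment outline of planned numbers. A reader might also infer from the adherence exclusion in 12.4 that the completion rate is 100% by construction. That exclusion is tied to sham-training sessions and 12-month testing, neither of which this trial has, and 9.4 gives this trial its own threshold.

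**Conclusion.** The inconsistency is real and lies in current text: 3.1, 7.2 and 8.6 cannot all hold once a treated subject withdraws. At the plan's 10% dropout, 20 completers out of 20 treated has a probability of 12% if all loss follows treatment and 34% if half does. It is expected only if all loss precedes treatment, with about 22 randomised. These figures rest on independence, the assumed timing and every retained subject completing.

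The precision statement omits 18/20, the expected result when all loss follows treatment, where the two-sided interval does not exclude 75%. The handling of replaced subjects is undefined and can decide whether 75% is excluded.

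The consequence is limited. The plan sets no go/no-go rule, so a reader should not infer that a decision rule would fail or that the pilot cannot show feasibility. What is at issue is the described precision of the primary endpoint, how losses are counted in it, and when the study closes. It should be fixed, and the fix is easy.

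**What to change.** 1. **3.1 and 8.4:** state 20 treated subjects, with more randomised if untreated subjects are replaced, and about 18 to 20 expected completers depending on when dropout occurs. Drop the aim of 20 completers.
2. **7.2:** define end of study as the last scheduled visit of the last randomised subject.
3. **3.1 and 12.2:** replace (.75, 1) for 20/20 with the two-sided 90% interval (.861, 1), and say that it is two-sided. Add 18/20 (.717, .982) and 19/20 (.784, .997). The printed .75 must be corrected at the same time; otherwise 19/20 would show a better lower limit than 20/20. If replaced subjects are counted, add examples on the larger denominator, such as 20/21 (.793, .998) and 20/22 (.741, .984).
4. **9.4 and 12.2:** state that the denominator is all randomised subjects, including any who are replaced, with the rate among treated subjects as supportive. Use the 9.4 definition of a completer in 12.2.

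**Cost:** protocol and SAP wording only, with no extra patients or procedures. The stated and reported completion figures may be slightly less favourable.

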## Schematic of Study Design

Prior to Enrollment

Obtain informed consent. Screen potential participants by inclusion and exclusion criteria; obtain history, document.

Randomize

Visit 1, 0mo

Baseline assessments: Cognitive battery, study partner questionnaires, MRI

Study intervention, 0-3 mo

Arm 1: HD-tDCS+CCT  
3 blocks of 5 daily sessions, each session lasting 80 min, one block/month

Visit 2, 3mo

Cognitive battery, study partner questionnaires, MRI

Visit 3, 6 mo

Cognitive battery, study partner questionnaires

## 5.0 INTRODUCTION

### 5.1 Mild Cognitive Impairment

Mild cognitive impairment (MCI) is currently an area of considerable clinical and research interest because of the high rate of conversion from MCI to Alzheimer disease (AD) (Almkvist et al., 1998; Collie et al., 2000; Kluger et al. 1999; Morris et al., 2001; Petersen et al., 1999; 2001; Rubin et al., 1989; Shah et al., 2000; Wolf et al., 1998). Several studies have demonstrated that patients with MCI progress to AD at a higher rate (10 to 15% per year) than normal elderly patients (1 to 3% per year). Therefore, MCI patients are considered to be at a higher risk for AD. MCI may be classified as either amnestic or non-amnestic, with the primary clinical distinction being the presence of prominent memory impairment in the former, and the predominant involvement of cognitive domains different from memory in the latter. Accordingly, amnestic MCI likely represents a prodromal stage of Alzheimer's dementia (Petersen et al., 2001); it is distinguished by impairment of episodic memory, and when contrasted with normal aging amnestic MCI is associated with a high degree of memory impairment with little or no impairment in activities of daily living (ADLs) (de Leon et al., 1993; Petersen et al., 2001). Individuals with amnestic MCI do not meet the currently accepted clinical criteria for probable AD, but the high rate of conversion from amnestic MCI to AD makes early diagnosis and treatment an important clinical issue. In its earliest stages, AD manifests primarily as cognitive impairment; As AD progresses, there is further loss of cognitive abilities, a loss of functional independence, and the development of behavioral problems (Gauthier, 1998). Early diagnosis and treatment may delay the onset of these symptoms.

### 5.2 Current Standard of Care

Currently, no drug has proven effective in treatment of MCI. Cholinesterase inhibitors have not been shown to decrease risk of progression from MCI to dementia at 1 and 3 years (Lin et al., 2013; Petersen et al., 2005; Salloway et al., 2004). In addition, cholinesterase inhibitors have limited or no significant effects on cognitive function over the short term (<12 months) and may substantially increase adverse effects, based on a meta-analysis of 4 trials (1,960 participants) (Lin et al., 2013) and another meta-analysis of 9 trials (5,149 participants) (Russ et al., 2012). Consequently, cholinesterase inhibitors and memantine are not recommended for MCI treatment and there are currently no FDA-approved medications for MCI (Lin et al., 2013; Russ et al., 2012). Ginkgo biloba, a widely used herbal supplement to improve cognition and memory, has not been shown in randomized trials to prevent cognitive decline in those with MCI or normal cognition (Snitz et al., 2009). Similarly, testosterone supplementation in older men showed no benefit for cognitive function in a randomized controlled trial (Emmelot-Vonk et al., 2008).

From 1998 to 2019 there have been about 150 failed attempts at developing Alzheimer's drugs, including medications for the management of MCI. The 'Amyloid Hypothesis' has been the leading scientific framework for the development of AD cures, and despite recent setbacks, a countless number of biologically specific AD treatments are currently being tested in clinical trials and in the drug development pipeline (Cummings et al., 2018). The recent high-profile failures highlight the importance of developing therapies that go beyond the targeting of amyloid and tau in order to help restore alternative physio-pathologic mechanisms; this would include changes in metabolism, innate immunity, modifiable lifestyle factors, and abnormal patterns of brain network connectivity and plasticity.

[figure not shown]
The restoration of brain network connectivity and of the brain's intrinsic plastic properties seems particularly relevant considering recent findings suggesting that adult hippocampal neurogenesis is active in adult healthy subjects and drops markedly in patients with AD (Moreno-Jimenez et al., 2019; Boldrini et al., 2018).

